10.1.4 Visit 7 (Week 2)

The Visit 2 (Day 1) hematology laboratory assessment and the test results for additional hematology test performed prior to the second sarilumab administration for Dose Regimen 1 and 2 Cohort patients must be reviewed before the second dose of sarilumab injection scheduled at Visit 7 (Day 15, Week 2) to confirm that the ANC and platelet count are not within the protocol-defined limits for temporary or permanent discontinuation of study drug. If a local laboratory was used for the additional hematology test at Visit 6 (Day 12 \pm 1 Day), a central laboratory sample for hematology should be drawn pre-IMP administration at this visit as scheduled for Dose Regimen 1 and 2 Cohorts.

- Record all concomitant medications use with start date and dose in the patient's e-CRF
- Inquire regarding AEs/SAEs
- Check home diary/compliance for Dose Regimen 3 Cohort patients
- Provide home diary to Dose Regimen 3 Cohort patients to record information pertaining to injections performed at home (date, time, injection location, and any problems) at each intermediate on-site visit. The completed diary will be reviewed at the next scheduled visit
- Perform the joint count assessments to note JIA disease manifestations (articular and extra-articular) and assess disease activity
- Complete the physician global assessment of disease activity
- Ask the patient/parent(s)/guardian(s) to complete relevant questionnaires: functional ability determined by CHAQ and (parent or guardian)/patient assessment of overall well-being. All questionnaires should be documented in the subject's study file. Each VAS score should be copied on the patient's e-CRF
- Perform a tuberculosis risk assessment. In case of suspicion of tuberculosis, refer the patient to a specialist for a complete examination and additional work-up
- Collect blood for hematology (see [Section 9.3.4](#)), chemistry including ALT, AST, ALP, total bilirubin, conjugated bilirubin, unconjugated bilirubin, and albumin
- Collect blood samples for hs-CRP and serum sarilumab (see [Section 9.1](#) and the study flow chart [Section 1.2](#))

- Call IVRS to register the visit and get the treatment kit number(s) assigned to each patient along with the dose volume to be administered
- Dispense the IMP to those patients who are at the Dose Regimen 3 Cohort for home injection
- Administer the IMP
 - Patients should be monitored for at least 30 minutes after each IMP administration for any signs or symptoms of a hypersensitivity reaction
- Check local tolerability (see [Section 9.3.3](#))
- Schedule the appointment for Visit 8 (Day 29, Week 4) and request the patient to come in fasting condition.

10.1.5 Visit 8 (Week 4)

- Record all concomitant medications use with start date and dose in the patient's e-CRF
- Inquire regarding AEs/SAEs
- Check home diary/compliance for Dose Regimen 3 Cohort patients
- Record vital signs including body temperature, BP and HR
- Perform a complete physical examination including skin, nasal cavities, eyes, ears, respiratory, cardiovascular, gastrointestinal, lymphatic examinations, complete neurological examinations, and musculoskeletal systems.
- Perform the joint count assessments to note JIA disease manifestations (articular and extra-articular) and assess disease activity.
- Provide home diary to Dose Regimen 3 Cohort patients to record information pertaining to injections performed at home (date, time, injection location, and any problems) at each intermediate on-site visit. The completed diary will be reviewed at the next scheduled visit
- Ask the patient/parent(s)/guardian(s) to complete relevant questionnaires: functional ability determined by CHAQ and (parent or guardian)/patient assessment of overall well-being. All questionnaires should be documented in the subject's study file. Each VAS score should be copied on the patient's e-CRF
- Complete the physician global assessment of disease activity
- Perform a tuberculosis risk assessment. In case of suspicion of tuberculosis, refer the patient to a specialist for a complete examination and additional work-up
- Collect blood for hematology (see [Section 9.3.4](#)), chemistry including ALT, AST, ALP, total bilirubin, conjugated bilirubin, unconjugated bilirubin, and albumin, fasting lipid, and hs-CRP
- Collect blood samples for serum sarilumab (see [Section 9.1](#) and the study flow chart [Section 1.2](#))

- Perform urine pregnancy test locally for female patients who have commenced menstruating
- Call IVRS to register the visit and get the treatment kit number(s) assigned to each patient along with the dose volume to be administered
- Dispense the IMP to those patients who are at the Dose Regimen 3 Cohort for home injection
- Administer the IMP
 - Patients should be monitored for at least 30 minutes after IMP administration for any signs or symptoms of a hypersensitivity reaction.
- Check local tolerability (see [Section 9.3.3](#))
- Schedule the appointment for Visit 9 (Week 6).

10.1.6 Visit 9 (Week 6), Visit 10 (Week 8), Visit 11 (Week 10)

- Record all concomitant medications use with start date and dose in the patient's e-CRF
- Inquire regarding AEs/SAEs
- Check home diary/IMP compliance
- Provide home diary to Dose Regimen 3 Cohort patients to record information pertaining to injections performed at home (date, time, injection location, and any problems) at each intermediate on-site visit. The completed diary will be reviewed at the next scheduled visit
- Record vital signs including body temperature, BP and HR at Visit 10 (Week 8)
- Perform a complete physical examination including skin, nasal cavities, eyes, ears respiratory, cardiovascular, gastrointestinal, lymphatic, neurological systems, and musculoskeletal systems at Visit 9 (Week 6)
- Perform the joint count assessments to note JIA disease manifestations (articular and extra-articular) and assess disease activity
- Ask the patient/parent(s)/guardian(s) to complete relevant questionnaires: functional ability determined by CHAQ and (parent or guardian)/patient assessment of overall well-being. All questionnaires should be documented in the subject's study file. Each VAS score should be copied on the patient's e-CRF
- Complete the physician global assessment of disease activity
- Perform a tuberculosis risk assessment. In case of suspicion of tuberculosis, refer the patient to a specialist for a complete examination and additional work-up
- Collect blood for hematology (see [Section 9.3.4](#)), chemistry including ALT, AST, ALP, total bilirubin, conjugated bilirubin, unconjugated bilirubin, and albumin
- Collect blood for hs-CRP at Visit 9 (Week 6), Visit 10 (Week 8), and Visit 11 (Week 10)

- Collect blood samples for serum sarilumab at Visit 10 (Week 8) (see [Section 9.1](#) and the study flow chart [Section 1.2](#))
- Perform urine pregnancy test locally for females who have commenced menstruating at Visit 10 (Week 8)
- Call IVRS to register the visit and get the treatment kit number(s) assigned to each patient along with the dose volume to be administered
- Dispense the IMP to those patients who are at the Dose Regimen 3 Cohort for home injection
- Administer the IMP
 - For those patients or parents or caregivers who are willing and able to perform injections for the patients, the Investigator or delegate will provide the training regarding to preparation and injection of IMP starting from Visit 10 (Week 8). This training must be documented in the patient's study file. The patient or the parent(s)/guardian(s) or the caregiver(s) is allowed to administer the IMP for the patient under the supervision of the Investigator or his/her delegate at Visit 10 (Week 8), Visit 11 (Week 10) and Visit 12 (Week 12) during the core treatment phase. For the subsequent administrations at the extension phase, the patient or the parent(s)/guardian(s) or the caregiver(s) will be allowed to administer the IMP at home and will record information linked to this injection in the diary at the intermediate on-site visits
 - If the patient or the parent(s)/guardian(s) or the caregiver(s) who are unable or who are unwilling to administer IMP, arrangements must be made for a qualified site personnel and/or professional caregiver to administer IMP for the patient
 - Patients should be monitored for at least 30 minutes after IMP administration for any signs or symptoms of a hypersensitivity reaction
- Check local tolerability (see [Section 9.3.3](#))
- Schedule the appointment for the next visit and request the patient to come in fasting condition for Visit 12 (Week 12).

10.1.7 Visit 12 (Week 12)

- Record all concomitant medications use with start date and dose in the patient's e-CRF
- Inquire regarding AEs/SAEs
- Record vital signs including body temperature, BP and HR
- Record patient weight (kg) and height (cm)
- Check Tanner stage (see [Appendix F](#)) and menstruation status for female patients
- Check home diary/compliance for Dose Regimen 3 Cohort patients

- Provide home diary to all dose regimen cohort patients to record information pertaining to injections performed at home (date, time, injection location, and any problems) at each intermediate on-site visit. The completed diary will be reviewed at the next scheduled visit
- Perform a complete physical examination including skin, nasal cavities, eyes, ears respiratory, cardiovascular, gastrointestinal, lymphatic, neurological systems, and musculoskeletal systems
- Perform the joint count assessments to note JIA disease manifestations (articular and extra-articular) and assess disease activity (ensure JADAS -27 joints are included)
- Ask the patient/parent(s)/guardian(s) to complete relevant questionnaires: functional ability determined by CHAQ and (parent or guardian)/patient assessment of overall well-being. All questionnaires should be documented in the subject's study file. Each VAS score should be copied on the patient's e-CRF
- Complete the physician global assessment of disease activity
- Perform a tuberculosis risk assessment. In case of suspicion of tuberculosis, refer the patient to a specialist for a complete examination and additional work-up
- Collect blood for hematology (see [Section 9.3.4](#)), complete chemistry (including sodium, potassium, chloride, bicarbonate, BUN, glomerular filtration rate, creatinine, creatinine clearance, calcium, phosphate, total protein, albumin, ALT, AST, ALP, total bilirubin, conjugated bilirubin, and unconjugated bilirubin), fasting lipid, hs-CRP, ESR, ANA, and anti-dsDNA
- Collect blood samples for serum sarilumab and antibodies to sarilumab, IL-6 and total sIL-6R (see [Section 9.1](#) and the study flow chart [Section 1.2](#))
- Perform urine pregnancy test locally for female patients who have commenced menstruating
- Call IVRS to register the visit and get the treatment kit number(s) assigned to each patient along with the dose volume to be administered
- Dispense the IMP to those patients who will continue the treatment in the extension phase.
- Administer the IMP for patients who are going to enter the extension treatment phase.
 - Patients should be monitored for at least 30 minutes after IMP administration for any signs or symptoms of a hypersensitivity reaction
- Check local tolerability (see [Section 9.3.3](#))
- Schedule the appointment for the next visit, ie, Visit 13 (Week 16) for patients in the dose-finding and second portions
- Schedule the appointment for the next visit, ie, Visit 15 (Week 24) for patients in the third portion
- Patients who discontinue the study treatment prematurely will be assessed using the procedure planned for the EOT Visit (Visit 27). These patients will be asked to return for an additional PK assessment 2 weeks after the EOT (the additional PK assessment is only

applicable for patients in the dose-finding and second portions) and EOS assessment planned for Visit 28, 6 weeks after the EOT visit. Schedule the appointment for the next PK assessment and EOS visit for those study discontinuation patients, as applicable. Patients discontinuing treatment prematurely during the core treatment phase should continue to return for the study visits as protocol scheduled except the IMP administration.

10.1.8 Visit 88 - Pharmacokinetic (PK) Follow-up Visit (End-of-Treatment [EOT] + 2 Weeks)

Visit 88 is an additional sarilumab PK assessment visit and this visit is not applicable for patients enrolled in the third portion.

In the dose-finding and second portions, if a patient discontinues the study treatment prematurely during the core treatment phase (at or before Week 12), the patient is required to have a PK follow-up visit 2 weeks after the EOT assessment.

- Record all concomitant medication use with start date and dose in the patient's e-CRF
- Inquire regarding AEs/SAEs
- Collect blood samples for serum sarilumab (see [Section 9.1](#) and the study flow chart [Section 1.2](#)).

10.1.9 Extension Phase

In the dose-finding and second portions, only patients achieving at least a JIA ACR30 response at Week 12 will be permitted to continue to participate in the extension phase. During the extension phase:

- Patients who were enrolled to the selected dose regimen during the core treatment phase (either during the initial dose-finding portion or directly to the selected dose regimen in the second portion) will continue on the selected dose regimen during the extension phase and will be followed-up as noted in ([Section 1.2.2.1](#))
- Once the selected dose regimen has been determined, patients who were not assigned to the selected dose regimen will have their dose regimen adjusted to the selected dose regimen during the extension phase. Prior to dose adjustment, these patients will complete the assessments as noted in [Section 1.2.2.1](#). After the dose regimen is determined, the patients will have their dose regimen adjusted to the selected dose regimen at the time of their next regular scheduled visit (according to [Section 1.2.2.1](#)), which will be considered as the first visit (Visit 101 [Week 0]) as shown in the flow chart in [Section 1.2.2.2](#). These patients will then continue with the assessments as noted in [Section 1.2.2.2](#). All patients will remain on treatment until they have received up to a total of 144 weeks of sarilumab exposure calculated from Visit 12. A table to determine when the last on-treatment visit should occur and the weeks between the last on-treatment visit, and the EOT visit based on when the patient was changed to the selected dose regimen is provided in [Table 1](#). After the last on-treatment visit, patients will be scheduled for the EOT visit (Visit 27) and the EOS visit (Visit 28).

- Patients who are enrolled in the third portion with the selected dose regimen will be followed-up as noted in [Section 1.2.2.3](#).

10.1.9.1 Patients who remain on the current dose (the selected dose regimen) or recruited directly under the selected dose regimen in the second portion

For additional information on the procedures for patients who remain on the current dose (or who are recruited directly under the selected dose regimen [second portion]), see the flow chart in [Section 1.2.2.1](#).

10.1.9.1.1 Visit 13 (Week 16), Visit 14 (Week 20), Visit 15 (Week 24), Visit 16 (Week 32), Visit 17 (Week 40), Visit 18 (Week 48), Visit 19 (Week 60), Visit 20 (Week 72), Visit 21 (Week 84), Visit 22 (Week 96), Visit 23 (Week 108), Visit 24 (Week 120), Visit 25 (Week 132), and Visit 26 (Week 144)

- Record all concomitant medications use with start date and dose in the patient's e-CRF
- Inquire regarding AEs/SAEs
- Check home diary/compliance
- Provide home diary. All patients or their parents or guardians will record information pertaining to injections performed at home (date, time, injection location, and any problems)
- Record vital signs including body temperature, BP, and HR
- Record weight (kg)
- Record patient height at Visit 15 (Week 24), Visit 18 (Week 48), Visit 20 (Week 72), Visit 22 (Week 96), Visit 24 (Week 120), and Visit 26 (Week 144)
- Check Tanner stage and menstruation status at Visit 15 (Week 24), Visit 18 (Week 48), Visit 20 (Week 72), Visit 22 (Week 96), Visit 24 (Week 120), and Visit 26 (Week 144) (see [Appendix F](#))
- Perform a complete physical examination including skin, nasal cavities, eyes, ears respiratory, cardiovascular, gastrointestinal, lymphatic, neurological systems, and musculoskeletal systems at Visit 15 (Week 24), Visit 18 (Week 48), Visit 20 (Week 72), Visit 22 (Week 96), Visit 24 (Week 120), and Visit 26 (Week 144)
- Perform the joint count assessments to note JIA disease manifestations (articular and extra-articular) and assess disease activity (ensure JADAS -27 joints are included) at Visit 15 (Week 24), Visit 18 (Week 48), Visit 20 (Week 72), Visit 22 (Week 96), Visit 24 (Week 120), and Visit 26 (Week 144)
- Ask the patient/parent(s)/guardian(s) to complete relevant questionnaires: functional ability determined by CHAQ and (parent or guardian)/patient assessment of overall well-being at Visit 15 (Week 24), Visit 18 (Week 48), Visit 20 (Week 72), Visit 22 (Week 96), Visit 24 (Week 120), and Visit 26 (Week 144). All questionnaires should be documented in the subject's study file. Each VAS score should be copied on the patient's e-CRF

- Complete the physician global assessment of disease activity at Visit 15 (Week 24), Visit 18 (Week 48), Visit 20 (Week 72), Visit 22 (Week 96), Visit 24 (Week 120), and Visit 26 (Week 144)
- Perform a tuberculosis risk assessment. In case of suspicion of tuberculosis, refer the patient to a specialist for a complete examination and additional work-up
- Perform PPD tuberculin skin test for patients ≤ 5 years or QuantiFERON-TB test for patients > 5 years at Visit 18 (Week 48); Visit 22 (Week 96), and Visit 26 (Week 144). QuantiFERON-TB test will be considered in the younger group of patients (≤ 5 years) based on the local PPD availability, local regulation for PPD screening, and the Investigator's judgments
- Collect blood for hematology (see [Section 9.3.4](#)), chemistry including ALT, AST, ALP, total bilirubin, conjugated bilirubin, unconjugated bilirubin, and albumin
- Collect blood for fasting lipids at Visit 15 (Week 24), Visit 18 (Week 48), Visit 20 (Week 72), and Visit 22 (Week 96).
- Collect blood for hs-CRP at Visit 15 (Week 24), Visit 18 (Week 48), Visit 20 (Week 72), Visit 22 (Week 96), Visit 24 (Week 120), and Visit 26 (Week 144)
- Collect blood for ESR at Visit 15 (Week 24), Visit 18 (Week 48), Visit 20 (Week 72), Visit 22 (Week 96), Visit 24 (Week 120), and Visit 26 (Week 144)
- Collect blood for ANA/anti-dsDNA at Visit 15 (Week 24), Visit 18 (Week 48), Visit 20 (Week 72), and Visit 22 (Week 96)
- Collect blood samples for serum sarilumab, antibodies to sarilumab at Visit 15 (Week 24), Visit 18 (Week 48), Visit 20 (Week 72) Visit 22 (Week 96), Visit 24 (Week 120) (see [Section 9.1](#) and the study flow chart [Section 1.2](#))
- Perform urine pregnancy test locally for female patients who have commenced menstruating for each visit
- Call IVRS to register the visit and get the treatment kit number(s) assigned to each patient along with the dose volume to be administered
- Dispense the IMP
- Administer the IMP
 - During the course of the extension phase (starting at Visit 12), the IMP injection dose can be adjusted. Refer [Appendix B](#) for injection volume based on the patient's weight
 - Patients should be monitored for at least 30 minutes after IMP administration for any signs or symptoms of a hypersensitivity reaction
- Check local tolerability (see [Section 9.3.3](#))
- Schedule the appointment for the next visit and request patients to come in a fasting condition at Visit 15 (Week 24), Visit 18 (Week 48), Visit 20 (Week 72), Visit 22 (Week 96), Visit 24 (Week 120), Visit 26 (Week 144), and Visit 27 EOT (Week 156).

10.1.9.2 Patients who change to the selected dose regimen

For additional information on the procedures for patients who change to the selected dose regimen, see the flow chart in [Section 1.2.2.2](#).

In this section, “Day” means “Day at this dose,” and “Week” means “Week at this dose.”

10.1.9.2.1 Visit 101 (Week 0), Visit 102 (Week 2), Visit 103 (Week 4), Visit 104 (Week 6), Visit 105 (Week 8), and Visit 106 (Week 12)

- Tanner stage and menstruation status at Visit 101 (Week 0)
- Review the previous visit’s hematology laboratory assessment before the administration of the dose of sarilumab
- Record all concomitant medications use with start date and dose in the patient’s e-CRF
- Inquire regarding AEs/SAE
- Record vital signs including body temperature, BP, and HR
- Record weight (kg) at Visit 101 (Week 0), Visit 103 (Week 4), Visit 105 (Week 8), and Visit 106 (Week 12)
- Record height (cm) at Visit 101 (Week 0)
- Perform a complete physical examination including skin, nasal cavities, eyes, ears respiratory, cardiovascular, abdominal, lymphatic, neurological systems, and musculoskeletal systems at Visit 101 (Week 0), Visit 104 (Week 6), and Visit 106 (Week 12)
- Call IVRS to register the visit and get the treatment kit number(s) assigned to each patient along with the dose volume to be administered
- Perform the joint count assessments to note JIA disease manifestations (articular and extra-articular) and assess disease activity. Any abnormalities should be recorded and documented in prior medical/surgical history (ensure JADAS -27 joints are included)
- Ask the patient/parent(s)/guardian(s) to complete relevant questionnaires: functional ability determined by CHAQ and parent/patient assessment of overall well-being. All questionnaires should be documented in the subject’s study file. Each VAS score should be copied on the patient’s e-CRF
- Complete the physician global assessment of disease activity
- Perform a tuberculosis risk assessment. In case of suspicion of TB, refer the patient to a specialist for a complete examination and additional work-up
- Purified Protein Derivative tuberculin skin test for patients ≤ 5 years or QuantiFERON-TB test for patients > 5 years at Visit 101 (Week 0)
- Collect blood for hematology and complete chemistry profile (see [Section 9.3.4](#)) at Visit 101 (Week 0), Visit 102 (Week 2), Visit 103 (Week 4), Visit 105 (Week 8), and Visit 106 (Week 12)
- Collect blood for fasting lipids at Visit 101 (Week 0), Visit 103 (Week 4), and Visit 106 (Week 12)

- Collect blood for hs-CRP from Visit 101 to Visit 106.
- Collect blood for ESR, ANA/anti-dsDNA antibody at Visit 101 (Week 0) and Visit 106 (Week 12)
- Collect blood samples for serum sarilumab (see [Section 9.1](#) and the study flow chart in [Section 1.2.2.2](#)) at Visit 101 (Week 0), Visit 102 (Week 2), Visit 103 (Week 4), Visit 105 (Week 8), and Visit 106 (Week 12)
- Collect blood samples for antibodies to sarilumab (see [Section 9.1](#) and the study flow chart in [Section 1.2.2.2](#)) at Visit 101
- Perform local urine pregnancy test for the female patients who have commenced menstruation prior to exposure to the IMP at each visit (except Visits 102 [Week 2] and 104 [Week 6])
- Dispense the IMP
- Provide home diary for IMP/compliance
- Administer the IMP
 - Patients should be monitored for at least 30 minutes after IMP administration for any signs or symptoms of a hypersensitivity reaction
- Check local tolerability (see [Section 9.3.3](#))
- Schedule the appointment for the next visit

10.1.9.2.2 Visit 107 (Week 16), Visit 108 (Week 20), Visit 109 (Week 24), Visit 110 (Week 32), Visit 111 (Week 40), Visit 112 (Week 48), Visit 113 (Week 60), Visit 114 (Week 72), Visit 115 (Week 84), Visit 116 (Week 96), Visit 117 (Week 108), Visit 118 (Week 120), and Visit 119 (Week 132)

For detailed information on the procedures for patients who change to the selected dose regimen, see the flow chart in [Section 1.2.2.2](#).

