1.2.2 Extension phase

In the dose-finding and second portions, only patients achieving at least a JIA ACR30 response at Week 12 will be permitted to continue to participate in the extension phase.

During the extension phase:

- Patients who were enrolled to the selected dose regimen during the core treatment phase (either during the initial dose-finding portion or directly to the selected dose regimen in the second portion) will continue on the selected dose regimen during the extension phase and will be followed-up as noted in [Section 1.2.2.1](#))
- Once the selected dose regimen has been determined, patients who were not assigned to the selected dose regimen will have their dose regimen adjusted to the selected dose regimen during the extension phase. Prior to dose adjustment, these patients will complete the assessments as noted in [Section 1.2.2.1](#). After the dose regimen is determined, the patients will have their dose regimen adjusted to the selected dose regimen at the time of their next regular scheduled visit (according to [Section 1.2.2.1](#)), which will be considered as the first visit (Visit 101 [Week 0]) as shown in the flow chart in [Section 1.2.2.2](#). These patients will then continue with the assessments as noted in [Section 1.2.2.2](#). All patients will remain on treatment until they have received up to a total of 144 weeks of sarilumab exposure calculated from Visit 12. A table to determine when the last on-treatment visit should occur and the weeks between the last on-treatment visit, and the EOT visit based on when the patient was changed to the selected dose regimen is provided in [Table 1](#). After the last on-treatment visit, patients will be scheduled for the EOT visit (Visit 27) and the EOS visit (Visit 28).
- Patients who are enrolled in the third portion with the selected dose regimen will be followed-up as noted in [Section 1.2.2.3](#).

1.2.2.1 Flow chart for patients who remain on the current dose (selected dose regimen) from the dose-finding portion or recruited directly under the selected dose regimen in the second portion

Visit	Extension phase (up to 144 weeks of sarilumab exposure from V12)														Post-treatment follow-up (6 weeks)		
	V13	V14	V15	V16	V17	V18	V19	V20	V21	V22	V23	V24	V25	V26		V27 ^a	V28 ^b

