9.5 PHYSICAL EXAMINATION

A complete physical examination will be performed at the Screening Visit 1 (Day -28 to Day -1, up to 31 days), Visit 2 (Day 1, Week 0), Visit 8 (Week 4), Visit 9 (Week 6), and Visit 12 (Week 12) during the initial core treatment phase and at designated visits during the extension phase (see Section 1.2.2). Any clinically significant abnormalities should be reported in the patient e-CRF as medical history if observed at Visit 1 (Day -28 to Day -1, up to 31 days) and reported as an AE if observed at Visit 2 (Day 1, Week 0) and during subsequent visits. Any clinically significant physical examination abnormality known at the Screening visit should be reported as medical history and not an AE. Clinically significant abnormalities or worsening from Baseline reported after the Screening visit should be reported as AEs.

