#### *Medical and surgical history*

Medical and surgical history includes all the relevant findings within the life-time of the patient. These data will be coded to a Preferred Term (PT) and associated primary System Organ Class (SOC) using the version of the Medical Dictionary for Regulatory Activities (MedDRA) in use at Sanofi at the time of database lock (DBL).

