### ***Disease characteristics at baseline***

Disease characteristics at baseline include:

- Duration of pcJIA (weeks / months / years)
- For pcJIA only: Rheumatoid factor (Positive:  $\geq 15$  IU/mL, negative:  $< 15$  IU/mL)
- Absolute Neutrophil Count
- The following American College of Rheumatology (ACR) classification criteria components:
  - Number of joints with active arthritis
  - Number of joints with limited range of motion
  - hs-CRP and ESR
- Patient's assessment of physical function based on the Childhood Health Assessment Questionnaire (CHAQ)
- [REDACTED]
- For pcJIA, type of juvenile idiopathic arthritis (JIA) subset and medical history of uveitis

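### At Visits 101 to 106, findings from the JIA joint assessment are sent to prior medical history, against the protocol's own AE rules, so new findings in dose switchers can miss the safety tables

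*Protocol*

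**What the plan says.** Section 10.1.9.2.1 lists the procedures for "Visit 101 (Week 0), Visit 102 (Week 2), Visit 103 (Week 4), Visit 104 (Week 6), Visit 105 (Week 8") and Visit 106 (Week 12), with weeks counted at the new dose. Section 1.2.2 makes the switch visit the start of this series: "which will be considered as the first visit (Visit 101 [Week 0"]).

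The relevant bullet begins "Perform the joint count assessments to note JIA disease manifestations (articular and extra-articular) and assess disease activity" and continues "Any abnormalities should be recorded and documented in prior medical/surgical history (ensure JADAS -27 joints are included"). It carries no restriction to particular visits, so it applies at all six.

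For patients who stay on their dose, the matching bullet in Section 10.1.9.1.1 reads "Perform the joint count assessments to note JIA disease manifestations (articular and extra-articular) and assess disease activity (ensure JADAS -27 joints are included"), with no mention of medical history.

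Section 9.5, on physical examination, gives the opposite rule: "Clinically significant abnormalities or worsening from Baseline reported after the Screening visit should be reported as AEs". Section 10.4.2 requires every AE from consent to end of study to be entered on the AE pages.

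The SAP, in Section 2.1.1, states: "Medical and surgical history includes all the relevant findings within the life-time of the patient". The same section lists among the baseline disease characteristics: "For pcJIA, type of juvenile idiopathic arthritis (JIA) subset and medical history of uveitis".

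**The concern.** The step covers extra-articular as well as articular manifestations, and it is done in children who have already had months of treatment. Prior history is the right place for what is found before the first dose. It is the wrong place for something that first appears on drug.

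A site that works down its visit list could enter a new finding as history and nowhere else. The safety outputs are built from AE records, so that finding would be absent from them. It could also surface in a baseline table, where it would look as if it had been present before treatment.

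Only switchers are given this instruction while on drug. It falls in the 12 weeks when Section 6.1 promises them closer monitoring, and SAP Section 2.4.5 sets their data after dose adjustment apart for a separate safety summary.

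**Working it through.** The documents give no figure to reproduce. The check is a comparison of sections, followed by simple counts.

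**1. Where the history instruction appears in the joint-count step**

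| Protocol section | Visits | Timing | History instruction |
|---|---|---|---|
| 10.1.1 | Visit 1 | before first dose | yes |
| 10.1.2 | Visit 2 | before first dose | yes |
| 10.1.4 to 10.1.7 | Visits 7 to 12 | on treatment | no |
| 10.1.9.1.1 | Visits 13 to 26, regimen unchanged | on treatment | no |
| 10.1.9.2.1 | Visits 101 to 106, switchers | on treatment | **yes** |
| 10.1.9.3.1 | third-portion extension visits | on treatment | no |
| 10.1.10 | Visit 27 | end of treatment | no |

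The instruction stands at the two pre-dose visits and at one on-treatment block. That it was carried over from Baseline is an inference, but the pattern fits.

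**2. How long these patients have been treated** (Table 1 in Section 1.2.2.2)

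- Earliest switch: Visit 13, Week 16.
- Latest switch: Visit 26, Week 144. The last on-treatment visit is then Visit 105, Week 8 at the new dose: 144 + 8 = Week 152. Such a patient never reaches Visit 106.

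**3. How many planned patients are exposed** (Section 6.1: 6 evaluable per regimen and weight group)

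- One tested regimen selected: 2 non-selected regimens × 2 weight groups × 6 = 24.
- An intermediate regimen selected, which the protocol summary allows: 3 × 2 × 6 = 36.

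The actual number will be lower to the extent that patients fail JIA ACR30 at Week 12, because only responders enter the extension. It could be somewhat higher to the extent that more than 6 are enrolled per cell to reach 6 evaluable.

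**4. What happens to a finding entered only as history**

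- SAP 2.1.4.1 defines TEAEs as a subset of AEs, and searches for AESIs in the general and specific AE forms. A history record enters neither.
- SAP 2.4.5 summarises safety data after dose adjustment separately. The finding would be missing there too if it arose after the switch.
- SAP 2.4.1 tabulates medical history with the baseline characteristics. The definition in SAP 2.1.1 sets no onset limit at first dose, so nothing stated there would remove the record.

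**5. Which other rules are active at the same visits**

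- Section 10.1.9.2.1 also requires AE enquiry.
- Section 9.5 operates where a physical examination is done. The text of 10.1.9.2.1 names Visits 101, 104 and 106; the flow chart in 1.2.2.2, as extracted, also marks Visits 103 and 105.
- At the remaining visits the safeguard is the AE enquiry with Section 10.4.2.
- No section says which instruction prevails.

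**The case against.** The strongest reply is that this is a stray sentence surrounded by safeguards. AE enquiry is required at the same visits, Section 10.4.2 applies throughout, and Section 9.5 covers the visits with an examination. The sentence does not say history instead of an AE, so a finding could be entered in both places. The flow charts mark medical/surgical history at Screening only, and the switchers' chart has no such row. The e-CRF is not available to us, so whether a later history entry is possible is unknown. The SAP's lifetime wording can also be read as a look-back from baseline. All of this stands, and it is why the conclusion is that events can be misfiled. It does not remove the contradiction, because the text names history as the destination and does not mention the AE page.

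Some stronger readings are tempting, and the documents do not support them:

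- **That the comparison before and after the switch is biased towards fewer events.** No event rate is given. Visit 101 is itself the switch visit, and Section 8.1 places dosing after clinical procedures, so a finding misfiled there would be lost from the pre-switch data instead. Safety is descriptive, with no between-group testing planned. The text of SAP 2.4.11, on the post-adjustment analyses, is not visible to us.
- **That 24 × 6 = 144 examinations, or 1/24 = 4.2 percentage points per event, measures the harm.** The first counts exposure to a sentence, not events. It also fails because 24 is not a ceiling and late switchers have fewer than six of these visits. With 36 switchers, one event is 1/36 = 2.8 points.
- **That every abnormality at these visits goes to history.** The sentence belongs to the joint-count and JIA-manifestation step only.
- **That new uveitis is the obvious casualty.** Section 4.1 says it is typically asymptomatic at onset and needs slit-lamp screening, so a joint count would not ordinarily find it. Eyes fall under the physical examination, where Section 9.5 applies. The same fact does make AE enquiry a weak backstop for findings without symptoms.

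**Conclusion.** The point holds as an internal contradiction with a real route to lost safety data. Section 10.1.9.2.1 tells sites to file on-treatment findings from the joint and JIA-manifestation step as prior history at up to six visits between about Week 16 and Week 152, against Sections 9.5 and 10.4.2. New findings in switchers can therefore be recorded only as history and miss the TEAE and AESI outputs and the post-adjustment summary.

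The exposed group is about 24 planned patients if a tested regimen is selected, or 36 if an intermediate one is, before ACR30 failures. These counts assume the planned 6 evaluable per cell and the same kind of selection in both weight groups. How many findings would be misfiled, and with what effect on any incidence, cannot be stated from the documents. The sentence should be corrected because it is wrong as written and the correction is cheap, not because a bias has been shown.

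**What to change.** **Protocol 10.1.9.2.1.** From "Any abnormalities should be recorded and documented in prior medical/surgical history (ensure JADAS -27 joints are included") delete everything before the bracket and keep the JADAS-27 reminder. Add: *Clinically significant new or worsened abnormalities are reported as AEs per Sections 9.5 and 10.4.2; joint counts remain efficacy data.* The words *clinically significant* are needed. Without them every newly active joint would become an AE, and efficacy data would flow into the TEAE tables.

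**SAP 2.1.1.** Limit the medical-history table, including uveitis history, to findings with onset before the first IMP dose.

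**Data management.** Query any medical-history record with an onset date on or after the first dose. This also finds records already misfiled.

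The cost is one sentence in the protocol, one clause in the SAP and one edit check. No procedure, visit or sample is added.
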